#### 6. Analysis Sets

#### 6.1 Safety Analysis Set

The Safety Analysis Set will consist of all subjects who received at least one dose of investigational product.

# 6.2 PK Concentration Analysis Set

The PK Concentration Analysis Set will contain all subjects who received at least one dose of etelcalcetide and have at least one PK sample collected.

### 6.3 PK Parameter Analysis Set

The PK Parameter Analysis Set will contain all subjects who received at least one dose of etelcalcetide and for whom at least one PK parameter can be adequately estimated.

### 6.4 Intent-to-treat Analysis Set

The Intent-to-treat Analysis Set (ITT) includes all subjects randomized. Subjects will be analyzed by randomized treatment. ITT Analysis Set will be used for study disposition summary.

#### 7. Planned Analyses

# 7.1 Interim Analysis and Early Stopping Guidelines

No formal interim analysis is planned.

# 7.2 Primary Analysis

The primary analysis for this study will occur when all subjects have completed all planned study procedures up to and including the EOS visit, as outlined in the Schedule of Assessments, and any follow up of a clinically significant clinical or laboratory abnormality and following database lock.

### 7.3 Final Analysis

Not applicable.

#### 8. Data Screening and Acceptance

#### 8.1 General Principles

The objective of the data screening is to assess the quantity, quality, and statistical characteristics of the data relative to the requirements of the planned analyses.

#### 8.2 Data Handling and Electronic Transfer of Data

The Amgen Global Study Operations-Data Management (GSO-DM) department will provide all data to be used in the planned analyses. This study will use the RAVE database.

Details of PK, antibody and external lab data transfers to the database are provided in the corresponding study data transfer plans.

### 8.3 Handling of Missing and Incomplete Data

Subjects may be missing specific data points for various reasons. In general, data may be missing due to a subject's early withdrawal from study, a missed visit, or non-evaluability of a data point at a particular point in time. Sites will be queried for missing or non-conformant data that are required or considered critical. All efforts will be made to capture complete critical data prior to the database lock.

The following imputation rules will be implemented for critical data if the missing or incomplete data cannot be resolved after the query process:

Only missing or partially missing dates for adverse events will be imputed with the exception of adverse events occurring prior to the first dose date. Stop dates for AEs will not be imputed. Adverse events with a partially missing start date that is conclusively prior to the date of first IP administered (as indicated by 'Did event start before first dose of IP' on the AE CRF page) will be considered pre-treatment adverse events and excluded from safety analyses. All other partially missing adverse event start dates will be handled as described below, with the reference date being Study Day 1:

- If the year is available and the day and month are missing, the day and month will be set to the 1st of January of the onset year
- If the year and month are available and the day is missing, the day will be set to the 1st of the onset month
- If the day and month are available and the year is missing, the year will be set to the year of the reference date
- If the year and day are available and the month is missing, the month will be set to January of the onset year
- If the resulting date is prior to the reference date, the date will be reset to the reference date (this applies to AE start date imputation only)

Partial/missing start dates for concomitant medications of interest will be imputed using the algorithm above with the reference date being Study Day 1. Partial/missing stop dates for these concomitant medications will be imputed using the following logic:

- If the medication stop date is completely missing, then the stop date is set as the end of the study date
- If the stop year is available and stop month and day are missing, the month and day will be reset to 31st of December of the stop year
- If the stop year and month are available and the stop day is missing, the stop day will be set to the last day of the month of the stop year
- If the stop year and day are available and stop month is missing, the stop month will be set to December of the stop year

Product: Etelcalcetide (AMG 416) Page 13 of 20

Protocol Number: 20140197 Date: 26 November 2018

- If the stop month and day are available and stop year is missing, the stop year will be reset to the year of the start date
- If any of the resulting dates are prior to the start date, the stop date will be reset to the start date
- If any of the resulting dates are after the end of study (EOS) date, the stop date will be reset to the EOS date

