### 9.6.9 Exposure to Concomitant Medication

The number and proportion of subjects receiving the following selected medications: nutritional vitamin D (vitamin D supplement), vitamin D sterol (active vitamin D), calcium supplements, and phosphate binder, will be summarized by treatment group at baseline and during the study.

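### When only the stop year of a calcium, vitamin D or binder record is missing, SAP 8.3 uses the start year, so a long-running drug stopped on study is dated as ending before the study

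*SAP*

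**What the plan says.** SAP 8.3 imputes partial stop dates for the medications of interest, which SAP 5.4 lists as nutritional vitamin D, active vitamin D, calcium supplements and phosphate binders. The rules apply only to what querying the site has failed to resolve. By missing component:

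- Whole date missing: end of study date.
- Day and month missing: 31 December of the stop year.
- Day missing: last day of the stop month.
- Month missing: December of the stop year.
- Year missing: "the stop year will be reset to the year of the start date".

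Two safeguards follow. "If any of the resulting dates are prior to the start date, the stop date will be reset to the start date"; and if the result is later than EOS, "the stop date will be reset to the EOS date".

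The dates feed SAP 9.6.9, where the number and proportion of subjects on each class "will be summarized by treatment group at baseline and during the study".

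Protocol 7.2.1 collects prior medication from 4 weeks before consent, and Protocol 6.5 collects concomitant therapy from consent to EOS, with start and stop dates. Protocol 3.1 makes calcium supplements, active vitamin D sterols and phosphate binders standard of care for all subjects, as prescribed by the investigator.

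**The concern.** A drug appears on these forms because it was in use at some time from 4 weeks before consent onwards, so its stop cannot lie years before that. Yet the missing-year rule puts it there whenever the drug began in a much earlier calendar year, which is to be expected for long-term background therapy in dialysis patients.

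The rule also runs against the others in its list. Every other stop rule takes the latest date compatible with what is known, subject to the EOS cap. A record with no stop date at all is carried to the end of the study and keeps the subject in the table. A record with a known day and month but no year can remove the subject. More information gives a worse answer.

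At stake is the by-arm summary of drugs that act on calcium and phosphorus, in a trial where corrected calcium is a named secondary safety measure (Protocol 10.1.1.2).

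**Working it through.** The plan states no figure on this point, so the check is to apply the rules to cases.

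**Inputs.** Stop rules and safeguards from SAP 8.3; collection window from Protocol 7.2.1 and 6.5; 22-day screening and 55-day study period from Protocol 3.5.1; about 24 and 8 subjects per arm from Protocol 3.3.

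**Assumptions.** Baseline use means start before Day 1 and stop on or after Day 1. On-study use means any day from Day 1 to Day 55. The calendar dates are illustrative.

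**Collection window.** With one screening period it opens at most 22 + 28 = 50 days before Day 1 and lasts at most 28 + 22 + 55 = 105 days. For Day 1 on 4 March 2019 it opens no earlier than 13 January 2019, and EOS is 27 April 2019.

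**Cases, each with a true stop on study and the stop year missing.**

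| Case | Start | Day 1 | Stop as recorded | Stop under SAP 8.3 | Baseline | On study |
|---|---|---|---|---|---|---|
| A | 10 May 2016 | 4 Mar 2019 | 1 April | 1 Apr 2016, before start, so reset to 10 May 2016 | lost | lost |
| B | 10 Jan 2016 | 4 Mar 2019 | 1 April | 1 Apr 2016 | lost | lost |
| C | 10 Jan 2019 | 4 Mar 2019 | 1 April | 1 Apr 2019 | kept | kept |
| D | 1 Dec 2018 | 20 Dec 2018 | 20 January | 20 Jan 2018, before start, so reset to 1 Dec 2018 | lost | lost |
| E | 24 Dec 2018 | 20 Dec 2018 | 20 January | 20 Jan 2018, before start, so reset to 24 Dec 2018 | not applicable | kept, shortened |

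In A and B the imputed stop is more than two years before the window opens. In A the first safeguard fires and moves the stop only to 2016; in B neither fires. In D the stop is wrong and before Day 1, although it need not be outside the window. C and E mark the limits: a start in the same calendar year as the stop gives the right date, and a start on or after Day 1 with its year known stays in the on-study count.

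**How often the rule fails once it is triggered.** Take every Day 1 in calendar year 2019 and every true stop from Day 1 to Day 55.

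- Start 1, 2 or 3 years before Day 1: 100% of such records lose their on-study use.
- Start 30 days before Day 1: 15.6%, all where start and stop fall either side of 1 January.
- Start in the same calendar year as the stop: none.

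These are shares of records that already have this pattern. They do not estimate how often it occurs; the documents give no figure for that.

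**Effect on the table.** One subject is 1/8 = 12.5 points in the placebo arm and 1/24 = 4.2 points in the active arm, and only if no other record in the same class covers the period.

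**Check of the alternative.** Take the latest year that gives a date on or before EOS and not before the start. A, B and C become 1 April 2019; D and E become 20 January 2019 (EOS 12 February 2019). All five are right. The reason is general: the window is much shorter than a year, so the same day and month one year later falls after EOS, and only one year is possible.

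**The case against.** The case against acting is mainly one of scale, and most of it stands. The pattern needs a known day and month with an unknown year, still unresolved after querying. Concomitant medications are assessed at every visit (Protocol 7.3.18) and participation lasts about 77 days, so an on-study stop should be recorded close to when it happens. SAP 9.6.9 counts subjects per class, so a second record in the class can leave the count unchanged. If baseline use is taken from the prior-medication entries at screening and Day -2 and not from dates, the baseline count is untouched. The table is descriptive and no covariate-adjusted analysis uses it. None of this makes the imputed date right.

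A reader might go further and infer a second error on the start side. A missing start day becomes the 1st of the month, and the reset to Study Day 1 is limited ("this applies to AE start date imputation only"), so new on-study starts might seem to be moved to baseline or hidden. The documents do not support that. The limit is explicit, and it is defensible for standard-of-care drugs that often predate Day 1 and whose baseline use is itself tabulated. A blanket reset would turn a start recorded only as 2016 into a Day 1 start and erase true baseline use. Over true starts on Days 2 to 55 with the day missing, 25.5% are dated before Day 1, but none leaves the on-study count when the stop date is complete or entirely missing. At most the subject is also counted at baseline. A conditional reset would be a refinement, not the correction of an error.

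**Conclusion.** The missing-stop-year rule is wrong as written. For a background drug begun in an earlier calendar year and stopped on study, it gives a stop date before Day 1, usually one that the collection window rules out. Neither safeguard repairs this, and the rule conflicts with the other stop-date rules in the same section.

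The importance is minor. The change worth making is to a rule, not to a result: few records are likely to be touched, and a percentage in the SAP 9.6.9 table may move by 12.5 or 4.2 points per affected subject. The loss from both periods rests on the date-overlap reading of two terms that the SAP does not define. It would be wrong to conclude that every partial date shifts a percentage, or that the start-date rules share the fault.

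**What to change.** Replace the missing-year line in SAP 8.3 with a rule of this kind: if only the stop year is missing, use the latest year that gives a date on or before the EOS date and not before the start date; if no year does so, apply the existing resets. It would help to state in SAP 9.6.9 how use at baseline and use during the study are derived, since the effect of any imputed date depends on it.

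The cost is one line of SAP text for the rule, one sentence for the definitions and a small change to the imputation program. Trial conduct and data collection do not change.

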#### 8.4 **Detection of Bias**

Lack of protocol compliance and the potential for biased statistical analyses will be examined by assessing the incidence of important protocol deviations. The clinical study team will identify and document the criteria for important protocol deviations.

#### 8.5 **Outliers**

PK plasma concentration data will be evaluated for outliers by visual inspection, and decisions to re-assay individual samples will be made in accordance with PK evaluation practice.

#### 8.6 **Distributional Characteristics**

There are no distributional requirements for the planned analyses. Therefore no assessment will be made.

#### 8.7 Validation of Statistical Analyses

Programs will be developed and maintained, and output will be verified in accordance with current risk-based quality control procedures.

Tables, figures, and listings will be produced with validated standard macro programs where standard macros can produce the specified outputs.

The production environment for statistical analyses consists of Amgen-supported versions of statistical analysis software; for example, the SAS System version 9.4 or later.

#### 9. Statistical Methods of Analysis

#### 9.1 **General Considerations**

Demographics, baseline characteristics, and safety data will be summarized by treatment groups. Unless otherwise stated, the data analysis will be conducted using subjects in the Safety Analysis Set. Descriptive statistics on continuous measurements will include mean, median, standard deviation, and range, while categorical data will be summarized using frequency counts and percentages. Graphical summaries of the data may also be presented. When data are summarized by time, the values recorded against the scheduled time points listed in the protocol will be used. Descriptive

summaries will be provided to characterize all primary and secondary endpoints in this study.

### 9.2 Subject Accountability

The number and percent of subjects who received investigational product, completed investigational product, discontinued from investigational product (including reasons for discontinuing), completed study, or discontinued the study (including reasons for discontinuing) will be summarized. The number of subjects included in and excluded from each analysis set will be summarized. Key study dates for the first subject enrolled, last subject enrolled and last subject's EOS will be presented.

# 9.3 Important Protocol Deviations

Important Protocol Deviations (IPDs) categories are defined by the study team before the first subject's initial visit and updated during the IPD reviews throughout the study prior to database lock. These definitions of IPD categories, subcategory codes, and descriptions will be used during the course of the study. Eligibility deviations are defined in the protocol.

#### 9.4 Demographic and Baseline Characteristics

Demographics data including sex, age, race, ethnicity and BMI will be summarized for each treatment using descriptive statistics. The same analysis will be performed for baseline characteristics and medical history.

# 9.5 Pharmacokinetic Endpoints

Plasma concentrations of etelcalcetide will be determined using a validated assay from PK Concentration Analysis Set. Individual and mean plasma concentration-time plots for etelcalcetide will be presented.

The PK parameters (ie, Cmax, AUClast) will be estimated using noncompartmental methods. Nominal dose and actual sampling time data will be used for calculation of PK parameters. Summary statistics will be generated for each PK parameter. Due to the effect of hemodialysis on the plasma concentration of etelcalcetide, AUClast is specifically defined in this study, as the area under the concentration-time curve during the time interval between dose administration and the beginning of the subsequent hemodialysis treatment.

The PK Parameter analysis set will be used in the analyses for the primary endpoint.

# 9.6 Safety Analyses

#### 9.6.1 Adverse Events

The Medical Dictionary for Regulatory Activities (MedDRA) version 20.0 or later will be used to code all events categorized as adverse events to a system organ class and a preferred term.

The adverse event grading scale to be used for this study will be the Common Terminology Criteria for Adverse Events (CTCAE), version 4.0 or later.

Subject incidence of all treatment-emergent adverse events, will be tabulated by system organ class and preferred term. Tables of fatal adverse events, serious adverse events, adverse events leading to withdrawal from investigational product and treatment-emergent hypocalcemia (depending on number of subject incidences) and event of interest (EOI) will be provided. Besides, subject incidence of AEs will also be summarized for all treatment-related AEs, treatment-related serious AEs, treatment-related fatal AEs and treatment-related AEs leading to withdrawal of IP.

### 9.6.2 Clinical Laboratory Test Results

Serum albumin, iPTH, cCa and phosphorus measurements will be summarized by treatment group for all scheduled visits. Change and percent change from baseline may also be summarized for all post-baseline scheduled visits by treatment group, as applicable.

### 9.6.3 Vital Signs

Vital signs will be listed and reviewed for each subject. Depending on the size and scope of changes, summaries of vital sign data by treatment group at each protocol-specified time point may be provided.

### 9.6.4 Physical Measurements

Physical measurements will be summarized by treatment group at each protocol-specified time point.

#### 9.6.5 Electrocardiogram

The ECG measurements from this clinical study are to be performed per standard of care for routine safety monitoring, rather than for purposes of assessment of potential QTc effect. Since these evaluations may not necessarily be performed under the rigorous conditions expected to lead to meaningful evaluation of QTc data, summaries and statistical analyses of ECG measurements are not planned.

Subject level listing will be provided for all on-study ECG measurements.

### 9.6.6 Anti-drug Antibodies

The incidence and percentage of subjects who develop anti-etelcalcetide antibodies (binding) at any time will be tabulated.

### 9.6.7 Exposure to Investigational Product

Descriptive statistics will be calculated to describe the exposure to investigational product by treatment group. A listing of the unique manufacturing lot numbers, and a listing of the subjects administered each manufacturing lot number will be provided.

Summary statistics will be provided for: number of days on IP, the minimum and maximum weekly dose, the cumulative total dose, average weekly dose during the treatment period, and the number and percentage of subjects receiving each dose level (0mg, 5 mg or missing for etelcalcetide) of IP at each visit during the study.

## 9.6.8 Exposure to Other Protocol-specified Treatment

N/A

### 9.6.9 Exposure to Concomitant Medication

The number and proportion of subjects receiving the following selected medications: nutritional vitamin D (vitamin D supplement), vitamin D sterol (active vitamin D), calcium supplements, and phosphate binder, will be summarized by treatment group at baseline and during the study.

### 9.7 Exploratory Endpoints

# 10. Changes From Protocol-specified Analyses

There are no changes to the protocol-specified analyses.

Page 17 of 20

# 11. Literature Citations / References

Not applicable.

# 12. Prioritization of Analyses

Not applicable.

# 13. Data Not Covered by This Plan

Not applicable.

Page 19 of 20

# 14. Appendices

Page 20 of 20

# Appendix A. Reference Values/Toxicity Grades

Refer to the NCI Common Terminology Criteria for AEs (CTCAE) Version 4.0, published: May 28, 2009 (v4.03: June 14, 2010) for AE and lab shift grading and information. The CTCAE is available at the following link:

http://evs.nci.nih.gov/ftp1/CTCAE/About.html
